7.2.2. Best Overall Response and Overall Response Rate

For responses by IRC, the best overall response for each subject will be provided by the oncologist.

For investigator-reported responses, the best overall response is the best response recorded before and including the first PD, in the order of CR/CMR, PR/PMR, SD/NMR, PD/PMD, and NE. In the case of SD/NMR, assessment must meet the SD/NMR criteria at least once on or after Day 49. Subjects who fail to meet this criterion will have best response of PD/PMD if the next available assessment after the initial assessment indicates PD/PMD or will have best response of NE if there are no additional assessments available.

A subject is considered a responder if they have a best overall response of CR/CMR or PR/PMR.

The ORR is the proportion of responders. Subjects who do not have sufficient baseline or on-study response assessment information to be adequately assessed for response status will be included in the denominators in the calculation of ORR.

Best overall response as determined by the IRC will be summarized descriptively for subjects in Group A. The ORR as determined by the IRC and its 95% exact binomial CIs will be calculated for subjects in Group A. Confidence intervals will be calculated based on the exact method for binomial distributions. This is considered the primary efficacy analysis of the study.

Best overall response as reported by the investigator will also be summarized descriptively for subjects in Group A. The ORR as reported by the investigator and its 95% exact binomial CIs will be calculated for subjects in Group A. Confidence intervals will be calculated based on the exact method for binomial distributions.

Response data as determined by IRC and those as reported by the investigator will be analyzed when all subjects have received at least 1 postbaseline disease assessment, or have progressed, withdrawn from the study, or died.

7.2.3. Subgroup Analyses for Overall Response Rate

Subgroups will be formed based on the following subject characteristics and baseline variables:

• Age: \leq 65 years, > 65 years

Gender: male, femaleRace: White, Others

• Geographic region: Europe, North America, Rest of World

Subgroups may be further divided or combined based on emerging data. The ORR as determined by IRC and its 95% CIs will be provided for subjects in Group A for each subgroup. A forest plot will be created to summarize the variability in ORRs as determined by IRC for subjects in Group A across subgroups.

7.3. Analysis of the Secondary Efficacy Parameters

7.3.1. **Duration of Response**

Duration of response is defined as the time from first documented evidence of CR/CMR or PR/PMR until disease progression or death due to any cause among subjects who achieve an overall response (ie, CR/CMR or PR/PMR) as determined by revised response criteria for lymphomas (Cheson et al 2014). For responses assessed by IRC, the date of first response and date of disease progression will be provided by the oncologist for subjects who have achieved best response of CR/CMR or PR/PMR. For investigator-reported response data, the date of PD will be the timepoint at which progression is first recorded. Censoring of DOR will follow the same algorithm as the censoring of PFS (Section 7.3.2).

The total number of responders as determined by the IRC, the number of subjects whose disease progressed as determined by the IRC or who died, and the number of subjects censored will be summarized for subjects in Group A. The Kaplan-Meier estimation of median DOR as determined by the IRC and its 95% CIs will be provided for subjects in Group A.

The total number of responders as reported by the investigator, the number of subjects whose disease progressed as reported by the investigator or who died, and the number of subjects censored will also be summarized for subjects in Group A. The Kaplan-Meier estimation of median DOR as reported by the investigator and its 95% CIs will be provided for subjects in Group A.

7.3.2. Progression-Free Survival

Progression-free survival is defined as the time from the date of first dose of the study drug to the first documented disease progression as determined by revised response criteria for lymphomas (Cheson et al 2014), or death due to any cause, whichever occurs first. For responses assessed by the IRC, date of disease progression will be provided by the oncologist. For investigator-reported data, the date of PD will be the timepoint at which progression is first recorded. Censoring for PFS will follow the algorithm outlined in Table 1, which is based on the FDA Guidance for Industry: Clinical Trial Endpoints for the Approval of Cancer Drugs and Biologics (FDA 2007).

Table 1: Evaluation and Censoring of Progression-Free Survival

Situation	Outcome	Date of Progression or Censoring
No baseline tumor assessments	Censored	Day 1
No valid postbaseline response assessments	Censored	Day 1
Progression documented between scheduled response assessments	Progressed	Date of first overall response of PD
No progression	Censored	Date of last valid radiologic assessment (not NE and not missing)
Study discontinuation for undocumented progression	Censored	Date of last valid radiologic assessment (not NE and not missing)
Study discontinuation for toxicity or other reason	Censored	Date of last valid radiologic assessment (not NE and not missing)
New anticancer treatment started	Censored	Date of last valid radiologic assessment (not NE and not missing) on/before starting a new anticancer treatment
Death before first progressive response assessment	Progressed	Date of death
Death between adequate response assessments	Progressed	Date of death
Death or progression after 2 or more missed assessments	Censored	Date of last valid radiologic assessment (not NE and not missing)

NE = not evaluable; PD = progressive disease.

The number of subjects whose disease progressed as determined by the IRC or who died and the number of subjects censored will be summarized for subjects in Group A. The Kaplan-Meier estimation of median PFS as determined by the IRC and its 95% CIs will be provided for subjects in Group A.

The number of subjects whose disease progressed as reported by the investigator or who died and the number of subjects censored will also be summarized for subjects in Group A. The Kaplan-Meier estimation of median PFS as reported by the investigator and its 95% CIs will be provided for subjects in Group A.

7.3.3. Overall Survival

Overall survival is defined as the time from the date of first dose of study drug to death due to any cause. For subjects who are still alive at the time of the analysis, OS will be censored on the date the subject is last known to be alive.

The number of subjects who died and the number of subjects censored will be summarized for subjects in Group A. The Kaplan-Meier estimation of median OS and its 95% CIs will be provided for subjects in Group A.

7.3.4. Best Change in Target Lesion Size

For subjects with measurable lesions at baseline, target lesion sizes will be measured by sum of product of diameters. The best percentage change from baseline, defined as the largest decrease in target lesion sizes during the study, will be summarized, and a waterfall plot of the best percentage change will be generated for subjects in Group A using data from the IRC. Note that for subjects who only have increases in target lesion sizes from baseline, the smallest increase will be considered as the best change from baseline. For IRC, there will be 2 readers for each subject. The PET best response will be compared between the readers to determine whether an adjudicator is needed for the review. If there is no discordance, the results from the first radiology read (labeled with "RADIOLOGIST 1" in the data) will be used for the analysis. If there is discordance, an adjudication will be performed per the imaging Charter. The adjudicator will choose the read that he or she believes most accurately represents the PET best response. This is considered the "accepted read," and data from this reader will be used for the analysis. An indicator is provided to identify the read that is considered to be the accepted assessment in data from the IRC.

Best change in target lesion size as reported by the investigator will also be summarized. Target lesions considered "too small to measure" will be assigned a default value of 5 mm × 5 mm for purposes of this analysis. Likewise, target lesions identified as "not present" at postbaseline assessments will be assigned 0 mm for this analysis. In the event that a target lesion is unaccounted for in a particular postbaseline timepoint (ie, the assessment is missing or NE), then the overall sum of target lesions will not be evaluable for that postbaseline timepoint.

8. SAFETY AND TOLERABILITY

Sample data displays are provided in Appendix A.

8.1. General Considerations

Summary tables may be replaced with listings when appropriate. For instance, an AE frequency table may be replaced with a listing if it only contains a few unique preferred terms reported on relatively few subjects.

Unless otherwise stated, all AEs reported on the CRF will be included in the summaries.

8.2. Adverse Events

8.2.1. Adverse Event Definitions

A TEAE is any AE either reported for the first time or worsening of a pre-existing event after first dose of study drug. Analysis of AEs (as discussed below) will be limited to TEAEs, but data listings will include all AEs regardless of their timing in relation to study drug administration.

Adverse events will be tabulated by MedDRA PT and SOC. Severity of AEs will be graded using the NCI CTCAE version 4.03. The CTCAE reporting guidelines and grading details are available on the CTEP website.

The subset of AEs considered by the investigator to be related to study drug will be considered to be treatment-related AEs. If the investigator does not specify the relationship of the AE to study drug, the AE will be considered to be treatment-related. The incidence of AEs and treatment-related AEs will be tabulated. In addition, SAEs will also be tabulated.

Any missing onset date, causality, or severity must be queried for resolution. Unresolved missing causality and severity will be handled according to the following rules:

- An unresolved missing causality will be considered treatment-related.
- An unresolved missing severity will be identified as an unknown severity.

For purposes of analysis, all AEs will be considered TEAEs unless the AE can unequivocally be defined as not treatment-emergent. Therefore, a missing onset date will be considered treatment-emergent, with the following examples illustrating exceptions:

- If the stop/resolution date is before the first dose date on Day 1, then the AE will not be considered treatment-emergent.
- If both the month and day are missing, and the last day of the year is before the first dose date on Day 1, then the AE will not be considered treatment-emergent.
- If only the day is missing, and the last day of the month is before the first dose date on Day 1, then the AE will not be considered treatment-emergent.
- If only the day is missing, and the first day of the month is after the first dose date on Day 1, then the AE will be considered treatment-emergent.

8.2.2. Adverse Events of Special Interest or Adverse Events of Clinical Interest

Specific AEs, or groups of AEs, will be followed as part of standard safety monitoring activities.

- ALT \geq 5 × ULN
- AST \geq 5 × ULN
- Colitis
- Diarrhea > Grade 2
- Rash \geq Grade 2
- Intestinal perforation
- Pneumonitis
- Pneumocystis jirovecii infection
- CMV infection
- Herpes simplex virus infection
- Varicella zoster virus infection
- Exfoliative dermatitis

The number of subjects who experienced any TEAEs of special interest will be summarized by maximum severity. Time to onset of new or worsening Grade 3 or 4 AEs will be summarized for ALT, AST, neutropenia, colitis, intestinal perforation, pneumonitis, *Pneumocystis jirovecii* infection, CMV infection, herpes simplex virus infection, varicella zoster virus infection, and exfoliative dermatitis. For rash and diarrhea events, time to onset of new or worsening Grade 2 or higher AEs will be summarized. ALT, AST, and neutropenia will be summarized based on the laboratory data.

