#### 8.4. Adverse Events of Special Interest

Specific adverse events, or groups of adverse events, will be followed as part of standard safety monitoring activities. These events (regardless of seriousness) will be reported per the SAE reporting timelines (see Section 8.3.2).

- $ALT \geq 5 \times ULN$
- $AST \geq 5 \times ULN$
- Colitis
- Diarrhea  $\geq$  Grade 2
- Rash  $\geq$  Grade 2
- Intestinal perforation
- Pneumonitis
- *Pneumocystis jirovecii* infection
- CMV infection
- Herpes simplex virus infection
- Varicella zoster virus infection
- Exfoliative dermatitis

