2. STUDY INFORMATION, OBJECTIVES, AND ENDPOINTS

2.1. Protocol and Case Report Form Version

This SAP is based on INCB 50465-202 Protocol Amendment 3 dated 23 FEB 2017 and CRFs approved 16 NOV 2017. Unless superseded by an amendment, this SAP will be effective for all subsequent Protocol amendments and CRF versions.

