8.2.3. Adverse Event Summaries

An overall summary of AEs will include:

- Number (%) of subjects reporting any TEAEs
- Number (%) of subjects reporting any SAEs
- Number (%) of subjects reporting any Grade 3 or 4 TEAEs
- Number (%) of subjects reporting any TEAEs related to INCB050465
- Number (%) of subjects reporting any SAEs related to INCB050465
- Number (%) of subjects reporting any Grade 3 or 4 AEs related to INCB050465
- Number (%) of subjects who temporarily interrupted INCB050465 because of TEAEs
- Number (%) of subjects who permanently discontinued INCB050465 because of TEAEs
- Number (%) of subjects with INCB050465 dose reductions because of TEAEs

- Number (%) of subjects who had a fatal TEAE
- Number (%) of subjects reporting any TEAEs during QW schedule
- Number (%) of subjects reporting any SAEs during QW schedule
- Number (%) of subjects reporting any Grade 3 or 4 TEAEs during QW schedule
- Number (%) of subjects reporting any TEAEs related to INCB050465 during QW schedule
- Number (%) of subjects who temporarily interrupted INCB050465 because of TEAEs during QW schedule
- Number (%) of subjects who permanently discontinued INCB050465 because of TEAEs during QW schedule
- Number (%) of subjects with INCB050465 dose reductions because of TEAEs during QW schedule
- Number (%) of subjects who had a fatal TEAE during QW schedule

The following summaries will be produced by MedDRA term (if 10 or fewer subjects appear in a table, a listing may be appropriate):

- Summary of TEAEs by SOC and PT
- Summary of TEAEs by PT in decreasing order of frequency
- Summary of TEAEs by SOC, PT, and maximum severity
- Summary of Grade 3 or 4 TEAEs by SOC and PT
- Summary of INCB050465 treatment-related AEs by SOC and PT
- Summary of INCB050465 treatment-related AEs by SOC, PT, and maximum severity
- Summary of Grade 3 or 4 INCB050465 treatment-related AEs by SOC and PT
- Summary of TEAEs leading to death by SOC and PT
- Summary of treatment-emergent SAEs by SOC and PT
- Summary of treatment-emergent SAEs by PT in decreasing order of frequency
- Summary of INCB050465 treatment-related SAEs by SOC and PT
- Summary of TEAEs leading to INCB050465 dose reduction by SOC and PT
- Summary of TEAEs leading to INCB050465 dose interruption by SOC and PT
- Summary of TEAEs leading to discontinuation of INCB050465 by SOC and PT
- Summary of TEAEs during QW schedule by SOC and PT
- Summary of Grade 3 or 4 TEAEs during QW schedule by SOC and PT

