10.1. Changes to Protocol-Defined Analyses

Not applicable.

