3.2.2	Summary of Treatment-Emergent Adverse Events by MedDRA System Organ Class and Preferred Term	Safety	X	X
3.2.3	Summary of Treatment-Emergent Adverse Events by MedDRA Preferred Term in Decreasing Order of Frequency			X
3.2.4	Summary of Treatment-Emergent Adverse Events by MedDRA System Organ Class, Preferred Term, and Maximum Severity	Safety X		
3.2.5	Summary of Grade 3 or 4 Treatment-Emergent Adverse Events by MedDRA System Organ Class and Preferred Term	Safety	Safety X X	
3.2.6	Summary of INCB050465 Treatment-Related Adverse Events by MedDRA System Organ Class and Preferred Term	Safety	X	
3.2.7	Summary of INCB050465 Treatment-Related Adverse Events by MedDRA System Organ Class, Preferred Term, and Maximum Severity	Safety	X	
3.2.8	Summary of Grade 3 or 4 INCB050465 Treatment-Related Adverse Events by MedDRA System Organ Class and Preferred Term	Safety	X	
3.2.9	Summary of Treatment-Emergent Adverse Events With a Fatal Outcome by MedDRA System Organ Class and Preferred Term	Safety	X	X
3.2.10	Summary of Serious Treatment-Emergent Adverse Events by MedDRA System Organ Class and Preferred Term	Safety	X	X
3.2.11	Summary of Serious Treatment-Emergent Adverse Events by Preferred Term in Decreasing Order of Frequency	Safety	X	X
3.2.12	Summary of INCB050465 Treatment-Related Serious Adverse Events by MedDRA System Organ Class and Preferred Term	Safety	X	X
3.2.13	Summary of Treatment-Emergent Adverse Events Leading to INCB050465 Dose Reduction by MedDRA System Organ Class and Preferred Term	Safety	X	
3.2.14	Summary of Treatment-Emergent Adverse Events Leading to INCB050465 Dose Interruption by MedDRA System Organ Class and Preferred Term	Safety	X	
3.2.15	Summary of Treatment-Emergent Adverse Events Leading to Discontinuation of INCB050465 by MedDRA System Organ Class and Preferred Term	Safety	X	X
3.2.16	Summary of Selected Treatment-Emergent Adverse Events of Special Interest by Highest Grade	Safety		X
3.2.17	Summary of Time to Onset of Selected Treatment-Emergent Adverse Events of Special Interest	Safety		X
3.2.18	Summary of Treatment-Emergent Adverse Events During QW Schedule by MedDRA System Organ Class and Preferred Term	Safety	X	X

Table No.	Title	Population	Standard	In-Text
3.2.19	Summary of Grade 3 or 4 Treatment-Emergent Adverse Events During QW Schedule by MedDRA System Organ Class and Preferred Term	Safety	X	X
3.2.20	Summary of INCB050465 Treatment-Related Adverse Events During QW Schedule by MedDRA System Organ Class and Preferred Term	Safety	X	

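### As read, SAP 8.2.2 sets the diarrhea AESI one grade above Protocol 8.4 and above the SAP's own time-to-onset rule: a minor consistency correction, once the symbol is checked on the signed page

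*SAP*

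**What the plan says.** Protocol Section 8.4 includes "Diarrhea $\geq$ Grade 2" among the AESIs. SAP Section 8.2.2 repeats the protocol's list of events, but the diarrhea item reads "Diarrhea > Grade 2". In the same SAP list, the ALT, AST and rash items carry the greater-than-or-equal sign, as they do in the protocol.

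Two analyses are attached to the list in SAP Section 8.2.2:

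- A count by grade: "The number of subjects who experienced any TEAEs of special interest will be summarized by maximum severity". The matching output in SAP Appendix A is Table 3.2.16, "Summary of Selected Treatment-Emergent Adverse Events of Special Interest by Highest Grade".
- A time-to-onset summary (Table 3.2.17), with its own thresholds: "For rash and diarrhea events, time to onset of new or worsening Grade 2 or higher AEs will be summarized".

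On versions, SAP Section 2.1 states: "This SAP is based on INCB 50465-202 Protocol Amendment 3 dated 23 FEB 2017". SAP Section 10.1, which would record departures from protocol-defined analyses, says "Not applicable".

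**The concern.** A strict inequality and a greater-than-or-equal sign differ by exactly one grade. If the SAP bullet is the rule that decides which diarrhea events are AESIs, the AESI table starts at Grade 3, while the protocol's definition starts at Grade 2. Sites would report Grade 2 diarrhea as an AESI under Protocol 8.4, and the AESI table would then leave it out.

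The event is not a marginal one for this drug. Protocol Section 1.3 reports diarrhea and colitis as serious events in 3 subjects each among 46 in the earlier study, and names both among the events that led to discontinuation. Colitis is listed with no grade limit, so a Grade 2 event coded as colitis would count as an AESI while one coded as diarrhea would not.

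What is at stake is whether one AESI table agrees with the protocol definition and with its companion table.

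**Working it through.** There is no figure in the plan to reproduce. The check compares the definitions on the severity scale of Protocol Section 8.1.2, which uses Grades 1 to 4 and does not use Grade 5.

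**Step 1. Which diarrhea grades does each rule select?**

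| Rule | Grade 1 | Grade 2 | Grade 3 | Grade 4 |
|---|---|---|---|---|
| Protocol 8.4, AESI list | no | yes | yes | yes |
| SAP 8.2.2, AESI list (as read) | no | **no** | yes | yes |
| SAP 8.2.2, time to onset | no | yes | yes | yes |

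The only difference is Grade 2. The SAP list stands alone against the other two rules.

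**Step 2. Does a lag between protocol versions explain it?** The amendment summary (Protocol Appendix C) places the change of the diarrhea item to Grade 2 or higher in Amendment 2, dated 09 NOV 2016. The SAP is built on Amendment 3, dated 23 FEB 2017, and is itself dated 22 MAR 2018. The protocol threshold was therefore already in place, and version lag does not explain the difference.

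**Step 3. Is it a declared change?** No. SAP Section 10.1 records none, and Section 8.2.2 gives no reason for a narrower threshold.

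**Step 4. Is a difference between the AESI list and the time-to-onset rule normal in this SAP?** Partly. For colitis, intestinal perforation, pneumonitis, the listed infections and exfoliative dermatitis, the list has no grade limit and timing is restricted to Grade 3 or 4. In those cases the timed events are a subset of the listed ones. For rash the two thresholds are the same. For diarrhea, as read, the order is reversed: Grade 2 events would be timed in an AESI table without being AESIs. The SAP also pairs rash and diarrhea at one threshold in the timing rule but gives them different signs in the list.

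**Step 5. What does a literal reading do to the outputs?** Take a subject whose worst diarrhea is Grade 2:

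- Table 3.2.16 (AESIs by highest grade): not counted for diarrhea. If this is the subject's only AESI, the subject also drops out of any overall AESI count.
- Table 3.2.17 (time to onset): counted.
- Table 3.2.4, the output for "Summary of TEAEs by SOC, PT, and maximum severity": counted, with the grade shown.
- Tables 3.2.2 and 3.2.3 (treatment-emergent events by system organ class and preferred term, and by frequency): counted.
- Tables 3.2.13 to 3.2.15 (events leading to reduction, interruption or discontinuation): counted where applicable.
- Listing 2.7.2 (adverse events): listed.

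The effect is confined to the diarrhea entry, and any overall count, in one table.

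**The case against.** **The symbol may be a reading artefact.** The whole discrepancy is one character, and the SAP text shows other symbol damage. The duration formulas in Section 6.4 have lost their minus signs, and two subgroup bullets in Section 7.2.3 run together. The less-than-or-equal sign in the futility rule is rendered one way in Section 3 and another in Section 9.1. Intact signs on the neighboring bullets therefore do not prove that this one was read correctly. The SAP's own timing rule and the absence of any declared change both suggest that Grade 2 or higher was intended. This stands, and it is why the signed page has to be checked first.

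**The effect on Table 3.2.16 is inferred.** The shells are in a separate document, the title refers to selected events, and SAP Section 8.1 includes all reported adverse events in summaries unless stated otherwise. The table could have been specified to show all grades. This also stands: the omission follows from a literal reading of the list, not from a shell that can be inspected.

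**The AESI list and the timing rule need not match.** This is true in general, and neutropenia is timed without being listed at all. It weakens the internal comparison but leaves the conflict with Protocol 8.4 untouched.

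**Stronger readings to resist.** A reader might infer that Grade 2 diarrhea goes unreported. It does not, because the general tables and listings still show it. A reader might also connect the bullet with the dose-interruption guidance in Protocol Table 2 or with expedited reporting under Protocol 8.4. The SAP bullet governs neither.

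**Conclusion.** The inconsistency is real in the text as read. The SAP's AESI threshold for diarrhea conflicts with Protocol 8.4 and with the SAP's own time-to-onset rule, and nothing in the documents explains or declares it. It is a minor consistency correction. It touches one table, loses no data, and has no bearing on the efficacy analyses.

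The size cannot be given as a number of subjects. One might take the earlier study's floor of 20% for diarrhea of any grade, apply it to 100 Group A subjects (0.20 × 100 = 20), assume that 25% to 50% had a maximum of Grade 2, and arrive at 5 to 10 subjects. The documents do not support that figure. The Grade 2 share has no source. The 20% is a lower bound from 46 subjects with mixed lymphomas on daily doses of 5 to 45 mg, and this trial changed the regimen with the aim of reducing adverse events.

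The conclusion rests on two assumptions: that the signed SAP shows the strict inequality, and that Table 3.2.16 is filtered by the list in Section 8.2.2.

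**What to change.** 1. Check the diarrhea bullet in Section 8.2.2 of the signed SAP. If the page already carries the greater-than-or-equal sign, the text needs no change.
2. If it shows the strict inequality, change the bullet to diarrhea of Grade 2 or higher, in line with Protocol 8.4 and the SAP's timing rule.
3. In either case, confirm that the specification of Table 3.2.16 uses Grade 2 or higher for diarrhea, so that it agrees with Table 3.2.17.

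The cost is one symbol and a check of one table specification. No further data collection is needed. If a stricter AESI threshold was in fact intended, it should be stated with its reason in SAP Section 10.1.
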